[figure not shown]

Duke Cardiovascular Magnetic Resonance Center

Patient Care

Research

Education

- Confidential -

Version: 3/01/2016

Investigator Initiated Project Title:

Microvascular Dysfunction in Nonischemic Cardiomyopathy:
Insights From CMR Assessment of Coronary Flow Reserve

Center: Duke Cardiovascular Magnetic Resonance Center,
Division of Cardiology, Duke University Medical Center

NCT03249272

Investigators:

[name]

[name]

Study Synopsis

Study Title	Microvascular dysfunction in nonischemic cardiomyopathy: Insights from CMR assessment of coronary flow reserve
Primary Objective	
 To determine the prevalence of microvascular dysfunction (MVD) by a CMR measurement of whole-heart (global) perfusion reserve in subtypes of nonischemic cardiomyopathy
Secondary Objective	
 To compare the compare the CMR measurement of global perfusion reserve with regadenoson and adenosine To ascertain the relationship between microvascular dysfunction and other CMR metrics including regional myocardial scarring and perfusion
Study Design	
 Single-center, observational study
Planned Enrollment	
 30 patients with hypertrophic cardiomyopathy 30 patients with idiopathic dilated cardiomyopathy 15 controls with atypical chest pain

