Subject Selection Criteria	
Inclusion Criteria
 
 Men or women aged 18 years or older Cardiomyopathy patients 
 -Patients presenting for CMR with the clinical diagnosis of hypertrophic cardiomyopathy based on left ventricular wall thickness of at least ≥ 15 mm in the absence of any other cardiac or systemic cause of hypertrophy -Patients presenting for CMR with the clinical diagnosis of idiopathic dilated cardiomyopathy based upon left ventricular ejection fraction $\leq 40\%$, LV end-diastolic diameter ≥ 55 mm or left ventricular end-systolic diameter ≤ 45 mm, and the absence of coronary stenoses on angiography. Control patients with atypical chest pain 
 -Patients presenting for CMR evaluation of chest pain but without evidence of obstructive coronary artery disease either by coronary angiography or stress testing. 
Exclusion Criteria
 
 Decompensated heart failure or hemodynamic instability Prior coronary revascularization (PCI or CABG) or myocardial infarction (as evidenced by previously elevated CPK-MB or troponin levels) Accelerating angina or unstable angina Inability to physically tolerate MRI or implanted objects that are MRI incompatible Inability to provide written informed consent obtained at time of study enrollment. Severe claustrophobia Advanced heart block or sinus node dysfunction Hypersensitivity or allergic reaction to regadenoson or adenosine Hypotension Active bronchospasm or history of hospitalization due to bronchospasm History of seizures Recent cerebrovascular accident Use of dipyridamole within the last 5 days Contraindication to aminophylline Severe renal insufficiency with estimated glomerular filtration rate < 30 ml/min/ 1.73 m² Pregnant or nursing
Length of Study	
Projected duration of enrollment: 1-1.5 years
 
Projected duration of analysis and manuscript preparation: 0.5-1 year
 
Total study duration: ~2.5 years

Primary Endpoint	The primary endpoint will be the prevalence of MVD by CMR. The hypothesis is that global perfusion reserve will be significantly lower in patients with hypertrophic cardiomyopathy and idiopathic dilated cardiomyopathy than in controls with atypical chest pain. We also anticipate that differences in prevalence of MVD between the cardiomyopathy groups will be observed.

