We propose to study the prevalence of MVD in patients with hypertrophic cardiomyopathy and idiopathic dilated cardiomyopathy compared to controls with atypical chest pain. MVD will be assessed by CS-CMR and will be defined by presence of global perfusion reserve <2.0 , which is a standard threshold used in prior studies.² Based on our initial observations, we believe our measurement of MVD will clearly distinguish between patients with cardiomyopathy and control patients with atypical chest pain, who have normal coronary arteries and no evidence of ischemia. The prevalence of MVD will be greater than 50% for both HCM and IDCM, but will be different between patients with hypertrophic cardiomyopathy and idiopathic dilated cardiomyopathy.

Secondary Objectives

To demonstrate the generalizability of global perfusion reserve as measure of MVD, we will compare the CS-CMR measurement of global perfusion reserve with regadenoson versus that adenosine to demonstrate that they are similar. Specifically, the global perfusion reserve in all participants receiving regadenoson will be compared to those receiving adenosine using a two sample t-test. We will also explore whether differences within the subgroups are present (e.g. controls receiving regadenoson vs controls receiving adenosine; HCM patients receiving regadenoson vs HCM patients receiving adenosine; IDCM patients receiving regadenoson vs IDCM receiving adenosine). However, given the relatively small numbers, we expect the within subgroup comparisons to be mainly for the generation of hypotheses for subsequent studies.

Additionally, based on our initial observations, we anticipate that the presence and severity of MVD will be dependent on different morphological and functional characteristics in HCM and IDCM. Specifically we will examine:

- (1) the relationship between MVD and scarring
- (2) the relationship between MVD and regional perfusion defects
- (3) the relationship between MVD and LV morphologic characteristics (mass, volume, ejection fraction)

As a tertiary objective, we will also estimate the amount of interstitial fibrosis present in the myocardium of patients HCM and IDCM, compared to controls. Interstitial fibrosis will be estimated using MODified Look-Locker Inversion-recovery sequence (MOLLI) sequence, which is performed prior to and after contrast administration. We will attempt to discern if an association exists between MVD and increases in interstitial fibrosis.

Methods

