Patient Selection

We will recruit patients referred to the DCMRC with a documented history of hypertrophic cardiomyopathy or idiopathic dilated cardiomyopathy. Those agreeing to consent will be enrolled and undergo the multifaceted CMR protocol (**Figure 3**). Patients with history of coronary artery disease will be excluded.

To serve as controls, we will recruit patients referred for CMR for atypical chest pain. Only patients with low Framingham Risk (10% or less CHD risk at 10 years) and no history of CAD will be considered for recruitment. Controls will be excluded if they have evidence of obstructive coronary artery disease either by coronary angiography or stress testing.

Other Exclusion Criteria

Patients will also be excluded for the following reasons:

- Decompensated heart failure or hemodynamic instability
- Prior coronary revascularization (PCI or CABG) or myocardial infarction (as evidenced by elevated CPK-MB or troponin levels)
- Accelerating angina or unstable angina
- Inability to physically tolerate MRI or implanted objects that are MRI incompatible
- Inability to provide written informed consent obtained at time of study enrollment.
- Severe claustrophobia
- Advanced heart block or sinus node dysfunction
- Hypersensitivity or allergic reaction to regadenoson or adenosine
- Hypotension
- Active bronchospasm or history of hospitalization due to bronchospasm
- History of seizures
- Recent cerebrovascular accident
- Use of dipyridamole within the last 5 days
- Contraindication to aminophylline
- Hypersensitivity or allergic reaction to gadolinium contrast media
- Severe renal insufficiency with estimated glomerular filtration rate <30 ml/min/ 1.73 m²
- If they are pregnant or nursing

A detailed clinical history will be performed in all patients at the time of CMR. Information including age, gender, symptomatology, blood pressure, weight, height, and cardiac risk factors will be recorded. 12-lead ECGs will be obtained in all. Blood will be drawn for measurement of creatinine (point of care) and hematocrit. In women of childbearing potential, a serum HCG will be drawn.

Study Specific Procedures

Upon agreeing to participate in the study, subjects will be randomized to receive regadenoson or adenosine.

CMR Overview

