The CMR methodology and analysis to be used are fully described in the references. The entire scan procedure and scan time should take around 45 minutes. A cardiologist or fellow will supervise the scan, assess/triage patients, and initiate treatment if needed. A schematic of the imaging procedure is shown in **Figure 3**.

1. Standard Scout images of the heart leading to double oblique horizontal long axis view (4-Chamber) of the heart
2. Cine Image of the horizontal long axis view of the heart
3. Prescribed double oblique short axis view of the heart with first slice at the insertion points of the mitral valve in diastole.
4. Cine images of the short axis of the left ventricle from the base to and including the apex for entire LV coverage.

[figure not shown]

Figure 3. Multifaceted CMR examination

5. Cine images of the long axis views of the heart (2 chamber, 3 chamber, 4 chamber).
6. MOLLI images will be obtained prior contrast administration.
7. Coronary sinus imaging at rest as described in Figure 1.
8. Patients and controls will receive either (a) regadenoson (0.4 mg IV) injection over 10 seconds followed by saline flush or (b) adenosine $140 \mu\text{g}\cdot\text{kg}^{-1}\cdot\text{min}^{-1}$ x 3 minutes. During the injection or infusion, the participants will be monitored (continuous ECG and blood pressure monitoring) for 3-4 minutes. Half of the participants will receive Regadenoson, while the remainder will receive adenosine. Any serious adverse reactions during or after vasodilator stress will be recorded.
9. Stress perfusion images of 4-5 short axis slices (basal, mid, and apical) per heart beat for 60 heart beats beginning after 1-1.5 minutes after the regadenoson injection.
10. Bolus contrast injection of 0.1 mmol/kg of gadolinium contrast (gadoteridol or gadoteric acid) followed at 30 cc of saline flush beginning beginning after 1-1.5 minutes after regadenoson administration or after 2 minutes of adenosine infusion.
11. Coronary sinus imaging during stress (Figure 1).
12. In those receiving regadenoson, aminophylline (100 mg IV) will be administered over 30-60 seconds after completion of coronary sinus imaging. If bronchospasm is noted, participants will be treated with inhaled albuterol metered dose inhaler.
13. After a 15 minutes wait period, rest perfusion images of 4-5 short axis slices per heart beat for 60 heart beats using the identical imaging location and parameters as the stress perfusion images.

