$$\text{Global Perfusion Reserve} = \frac{\text{coronary sinus blood flow during maximal vasodilation}}{\text{coronary sinus blood flow at rest}}$$

Coronary sinus blood flow will be measured by contouring the coronary sinus at each time point within the cardiac cycle on both the magnitude and phase CS-CMR images at each cardiac frame. Total coronary sinus blood flow is then calculated by summing the flow per cardiac frame over the cardiac cycle. A global perfusion reserve of <2.0 will be regarded as abnormal and consistent with MVD.

Flow measurements will undergo a baseline correction using basal myocardium reference region located closest to the coronary sinus during at late-systole or mid-diastole when the motion is the most static. The baseline correction was performed for each cardiac frame to get the corrected coronary sinus blood flow. Coronary sinus blood flow_{corr}=V_{corr}×A_{CS}, where coronary sinus blood flow_{corr} is baseline corrected. V_{corr} comes from subtracting mean velocity of static region of interest from CS velocities. A_{CS} is area of CS at each time frame.

For the secondary aims, specific analyses will also be performed for each CMR technique to determine myocardial scar size, extent of regional perfusion defects, and morphological and function characteristics such as LV mass, LVEF, and LV volume.

Myocardial scarring will be determined by visual inspection using the American Heart Association 17-segment model. A patient is adjudicated to have myocardial scarring if there is at least more than one quarter of a myocardial segment of DE. This is done to reduce the effect of imaging artifacts, which can occasionally mimic DE. The extent of regional scarring is scored according to the spatial extent of delayed hyperenhancement within each segment (0 = no hyperenhancement (HE); 1 = 1%–25% HE; 2 = 26%–50% HE; 3 = 51%–75% HE; and 4 = 76%–100% HE). Global infarct size will be calculated by contouring of hyperenhanced regions from the stack of short-axis of delayed enhancement CMR images.

Regional myocardial perfusion will be scored by visual inspection using the American Heart Association 17-segment model (minus the apex) for the presence or absence of perfusion abnormalities and the spatial extent of hypoperfusion within each segment. Perfusion defect size will be calculated by contouring of hypoenhanced regions from stress perfusion CMR images.

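### Balance of regadenoson and adenosine within HCM, IDCM and controls is not specified, and the pooled agent comparison ignores diagnosis, at a cost mainly in precision

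*Combined protocol and SAP*

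**What the plan says.** Under Study Specific Procedures: "Upon agreeing to participate in the study, subjects will be randomized to receive regadenoson or adenosine". Step 8 of the CMR Overview adds the only balance target: "Half of the participants will receive Regadenoson, while the remainder will receive adenosine". Strata, blocks, concealment and the method of generating the list are not mentioned anywhere in the document.

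The Study Synopsis plans "30 patients with hypertrophic cardiomyopathy", "30 patients with idiopathic dilated cardiomyopathy" and "15 controls with atypical chest pain", 75 in all. It also states: "The primary endpoint will be the prevalence of MVD by CMR". Under Image Analysis one cut-off applies whichever agent was given: "A global perfusion reserve of <2.0 will be regarded as abnormal and consistent with MVD".

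The Secondary Objectives plan a two-sample t-test of GPR between agents over all participants, with the aim of showing that the agents are similar. They add comparisons within each diagnosis, for example "controls receiving regadenoson vs controls receiving adenosine", which the protocol describes as mainly hypothesis-generating because numbers are small.

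**The concern.** Agent allocation serves a secondary objective, but every participant's MVD status is read under the agent drawn. Diagnosis is the comparison factor of the primary endpoint and is known before allocation. The protocol also expects it to matter: the Primary Objective says the measure should clearly separate cardiomyopathy patients from controls, and the pilot found MVD in about 70% of HCM patients and in none of 3 controls.

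If the list is not balanced within diagnosis, controls can fall unevenly between the agents. Because controls are expected to have higher GPR, their distribution moves the pooled agent difference even when the agents are identical. That comparison is meant to support a claim of similarity, so a noisy estimate makes a real difference easier to miss. A chance difference in agent mix between HCM and IDCM could also enter the prevalence comparison, if the agents give different GPR.

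**Working it through.** **The plan's own figure.** The document gives none for agent balance. Its one power figure (71%, 25 per group, 25-point difference) is reproduced for an assumed 70% versus 95% at two-sided 0.05 (70.7% by the arcsine formula, 70.8% by exact enumeration of the uncorrected chi-square test). It has no agent term, so this point leaves it unchanged.

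**Inputs.** Group sizes of 30, 30 and 15 and the overall half split come from the protocol. Assumptions: one unstratified list with 37 participants on one agent and 38 on the other; mean GPR 1.7 in both cardiomyopathies and 2.8 in controls (gap 1.1); within-diagnosis SD 0.6.

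**1. Chance imbalance.** The counts on one agent are hypergeometric.
- Controls: SD = √(37 × 0.2 × 0.8 × 38/74) = 1.74. A split of 10/5 or worse has probability 0.249, and 11/4 or worse 0.082.
- HCM minus IDCM: each count has variance 37 × 0.4 × 0.6 × 38/74 = 4.56 and their covariance is −37 × 0.4 × 0.4 × 38/74 = −3.04. The SD of the difference is √(2 × 4.56 + 2 × 3.04) = 3.90 participants, or 3.90/30 = 13 points. By simulation, a difference of 20 points or more occurs in about 16% of trials.

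**2. Pooled agent comparison.**
- Part due to diagnosis mix: 1.1 × 1.74 × (1/37 + 1/38) = 0.102 GPR.
- Part due to spread within diagnosis: 0.6 × √(1/37 + 1/38) = 0.139.
- Total: √(0.102² + 0.139²) = 0.172, so the SD is 0.17 against 0.14, a ratio of 1.24.
- Range: a gap of 0.7 with SD 0.8 gives 0.196/0.185, or 6% wider. A gap of 1.4 with SD 0.5 gives 0.174/0.115, or 51% wider.

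Simulated for an assumed true agent difference of 0.4 GPR, two-sided 0.05:

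| Allocation | Analysis | Type I error | Power |
|---|---|---|---|
| One list | t-test | about 5% | 63% |
| One list | adjusted for diagnosis | about 5% | 80% |
| Within diagnosis | t-test | about 1.5% | 59% |
| Within diagnosis | adjusted for diagnosis | about 5% | 81% |

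**3. Primary comparison, HCM versus IDCM.** Assume the agents' MVD rates differ by 20 points. A 20-point mix difference then shifts the prevalence difference by 0.20 × 0.20 = 4 points. Over all trials the shift has mean zero and SD 0.20 × 13 = 2.6 points. The standard error at 30 per group is √(0.7 × 0.3/30 + 0.45 × 0.55/30) = 12 points for 70% versus 45%, and 9 points for 70% versus 95%. Simulated type I error at a common 70% rate stays at 4.8–4.9% for agent effects from 0 to 30 points.

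**4. Within-diagnosis agent comparisons.** The standard error relative to an equal split is √(1/a + 1/b)/√(4/(a + b)). This gives 1.06 for 10/5 or 20/10, and 1.13 for 11/4.

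**The case against.** The strongest objection is that silence is not evidence of a poor scheme. A split of 15/15, 15/15 and 7/8 also satisfies both allocation sentences. This stands: a reader might infer that the protocol randomises without regard to diagnosis, but it neither says nor excludes that. The imbalance figures describe what the wording permits.

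A reader might also infer that the primary comparison is biased. The documents do not support this. Allocation is random, so the shift has mean zero and type I error is not inflated. The protocol expects the agents to be similar, and no figure in it supports the 20-point agent effect assumed above.

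A third tempting reading is that the within-diagnosis agent comparisons are confounded. They are not: each compares randomised participants who share a diagnosis, and the protocol already limits what will be claimed from them.

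Finally, the pooled t-test is valid as planned under one list, because its variance already contains the spread between diagnoses. Adjustment alone recovers nearly all the lost precision (power 80%, against 81% with stratification as well). This also stands. Stratification chiefly guards the one realised trial against an awkward split, above all in the 15 controls.

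**Conclusion.** The point holds as a minor one: balance of agent within diagnosis should be specified, and the pooled agent comparison should account for diagnosis. Under the assumed means and SD, the planned comparison has an SD of 0.17 GPR where 0.14 is attainable. The loss depends on the gap between controls and cardiomyopathy patients, which the protocol expects but does not quantify. For the primary endpoint, the 4-point shift needs both an assumed 20-point agent effect and an imbalance seen in about 16% of trials, and it remains well below the standard error of 9 to 12 points. The within-diagnosis comparisons lose about 6% to 13% in standard error under the uneven splits considered.

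**What to change.** In Study Specific Procedures, state that participants are randomised 1:1 in concealed permuted blocks within HCM, IDCM and controls, giving 15/15, 15/15 and 7/8. This keeps the overall 37/38 split and reduces the difference in agent mix to 0 points between HCM and IDCM and about 3 points between either and controls (50% versus 7/15 = 47%).

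In Secondary Objectives, replace the unadjusted pooled t-test with a comparison adjusted for diagnosis, for example a linear model for GPR with agent and diagnosis. The two changes belong together: stratifying while keeping the unadjusted test makes it conservative (type I error about 1.5%) and gains no power.

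An agent-adjusted HCM-IDCM prevalence difference can be given as a sensitivity analysis. Stratifying the 15-control comparison by agent is not advised: with 7 and 8 controls and no MVD among the 3 pilot controls, empty event cells are likely.

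The cost is three short lists instead of one and a slightly more complex model, with no added participants, visits or scans. If stratification was already intended, one sentence settles the allocation part.

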14. Bolus contrast injection of 0.1 mmol/kg of gadolinium contrast (gadoteridol or gadoteric acid) followed at 30 cc of saline flush beginning at the start of rest perfusion imaging.
15. Delayed enhancement images
 - a. (Starting immediately after rest perfusion imaging) True FISP IR single shot non-breath held images (stack of short-axis views from base to apex with normal myocardium nulled). These are performed with the patient instructed to breath quietly with minimal respiratory motion
 - b. (Starting immediately after single shot True FISP IR) breath held, ECG gated, segmented inversion recovery FLASH sequence with inversion time adjusted to null the myocardium. Slice locations should be identical to cine CMR locations
 - c. Repeat step A (single-shot non breath-held stack of delayed enhancement images) with the TI fixed at 600 ms.
16. MOLLI images will be obtained after contrast administration.

CMR details and parameters

(1) Cine:

- SSFP cine sequences are ECG gated and breath held
- Slice Thickness of 6mm with a distance of 8 mm between slices (gap of 2 mm)
- Temporal resolution of less than 45 ms
- Flip angle maximized (>60 degrees)
- After obtaining horizontal long axis of the heart, obtain double oblique short axis at the level of

the insertion points of the mitral valve in diastole. Proceed with short axis cines every 10mm from the base to the apex until the myocardium is not visualized

(2) Coronary sinus at rest

A 3 step process was used to determine the optimal view for en face velocity encoded CMR of the CS. A graphical demonstration of the steps is shown in **Figure 1A-B**.

- Step 1: Acquisition of optimal CS-CMR imaging plane (Figure 1). In addition to the standard long axis cine planes, 2 additional orthogonal views (diaphragmatic 4-chamber, basal short-axis) are obtained to localize the coronary sinus. The diaphragmatic 4-chamber is obtained by adjusting the standard 4-chamber, inferiorly to visualize the CS entering into RA. A basal short axis is obtained based upon the location of the CS on the diaphragmatic 4-chamber. The optimal CS-CMR plane was acquired orthogonal to the CS in both in-plane views, within 1-2 cm of the CS ostium, ensuring the through-plane CS perpendicular to the main direction of the CS motion.

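### The two descriptions of the stress scan give incompatible timings, and the only stated adenosine duration (3 minutes) does not reliably cover the stress coronary sinus scan

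*Combined protocol and SAP*

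**What the plan says.** All references are to the combined protocol and SAP, under Methods.

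**CMR Overview**
- Step 8 gives adenosine "x 3 minutes. During the injection or infusion, the participants will be monitored (continuous ECG and blood pressure monitoring) for 3-4 minutes".
- Step 9 runs stress perfusion "per heart beat for 60 heart beats beginning after 1-1.5 minutes after the regadenoson injection"; it gives no start time for adenosine.
- Step 10 gives contrast "beginning after 1-1.5 minutes after regadenoson administration or after 2 minutes of adenosine infusion".
- Step 11 is the stress coronary sinus scan.
- Step 12 sets the reversal rule for one agent only: "In those receiving regadenoson, aminophylline (100 mg IV) will be administered over 30-60 seconds after completion of coronary sinus imaging".
- Step 13 runs rest perfusion "for 60 heart beats using the identical imaging location and parameters as the stress perfusion images".

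**CMR details and parameters**
- Item (3) has either agent followed by 3-4 minutes of monitoring with the table partly out of the bore. The table then goes in, contrast is given, and perfusion is imaged for 40-50 beats.
- Item (4) places the coronary sinus scan directly after stress perfusion and labels it as done under adenosine stress. It reuses the location and settings of the rest scan, which is a breath-hold sequence, and it repeats the aminophylline rule.

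**Image Analysis** defines global perfusion reserve as coronary sinus flow at maximal vasodilation divided by flow at rest. A value below 2.0 counts as microvascular dysfunction (MVD), whose prevalence is the primary endpoint.

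**The concern.** The stress coronary sinus scan supplies the numerator of the primary measurement. It comes last in the stress sequence, after contrast and perfusion imaging, so any slack or conflict in the earlier timings falls on it. For regadenoson the plan holds the reversal drug until that scan is finished. For adenosine the visible text gives a fixed 3 minutes and no rule linking the end of the infusion to the end of the scan.

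If the infusion stopped before or during the scan, stress flow could only be understated. Reserve would fall and more participants would be classed as having MVD, in the half given adenosine (75 / 2 = 37.5, so 37 or 38 of the planned 75). The same error would enter one arm only of the secondary regadenoson-adenosine comparison, which is meant to show that the agents give similar results. Without recorded times it could not be told apart from a drug difference.

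**Working it through.** The plan states no figure to reproduce. The check is a timeline, in seconds from the start of the vasodilator.

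**Inputs from the documents.** Adenosine 180 s. Overview contrast at 120 s (adenosine) or 60-90 s (regadenoson). Details contrast no earlier than 180-240 s (both). Stress perfusion 60 beats (overview) or 40-50 beats (details).

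**Assumptions.** Heart rate (HR) under stress is 60-100 bpm. Perfusion imaging starts with contrast: steps 9 and 10 give the same time for regadenoson, and step 14 starts rest contrast "of saline flush beginning at the start of rest perfusion imaging". Set-up plus one coronary sinus scan takes T = 15, 25 or 35 s, because the scan length is not stated.

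**1. Contrast times** (no heart rate needed).
- Adenosine: 180 - 120 = 60 s to 240 - 120 = 120 s.
- Regadenoson: 180 - 90 = 90 s to 240 - 60 = 180 s.

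The ranges do not overlap. Imaging cannot run while the table is out, so one instruction must be broken.

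**2. Details timeline, adenosine.** Scan start = contrast time + beats × 60 / HR.
- Earliest: 180 + 40 × 60 / 100 = 204 s.
- Latest: 240 + 50 × 60 / 60 = 290 s.
- Against a 180 s infusion, the scan starts 24 to 110 s after the infusion ends.

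Reading the 3-4 minutes in item (3) as the infusion length does not help, because contrast then comes at or after the end of the infusion.

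**3. Overview timeline, adenosine.** Time left = 180 - (120 + beats × 60 / HR).

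| Beats | 60 bpm | 75 bpm | 90 bpm | 100 bpm |
|---|---|---|---|---|
| 60 | 0 s | 12 s | 20 s | 24 s |
| 50 | 10 s | 20 s | 27 s | 30 s |
| 40 | 20 s | 28 s | 33 s | 36 s |

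**4. Heart rate needed for the scan to finish within 180 s.** HR = 60 × beats / (60 - T).

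| Beats | T = 15 s | T = 25 s | T = 35 s |
|---|---|---|---|
| 60 | 80 bpm | 103 bpm | 144 bpm |
| 50 | 67 bpm | 86 bpm | 120 bpm |
| 40 | 53 bpm | 69 bpm | 96 bpm |

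The 40-50 beat rows mix the overview's contrast time with the details section's beat count. They are the favourable case, and they conflict with the 60 beats in steps 9 and 13.

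**5. Infusion needed beyond 180 s**, overview timeline with 60 beats. Extra = 3600 / HR + T - 60, not below 0. For T = 15, 25 and 35 s:
- 60 bpm: 15, 25, 35 s
- 75 bpm: 3, 13, 23 s
- 100 bpm: 0, 1, 11 s

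**The case against.** The strongest reply is that the plan's intent is clear. Step 11 and item (4) both place the scan under stress, and the reserve formula calls for maximal vasodilation. Item (4) is coherent only if adenosine runs on through perfusion and the coronary sinus scan. A cardiologist or fellow supervises every scan. On this view the 3 minutes is loose wording that experienced staff would not follow to the second. The Overview also says "The CMR methodology and analysis to be used are fully described in the references" and refers to Figure 3 as a schematic of the procedure. Neither is available here, and either may show when the infusion stops.

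Most of this stands. A reader might infer that adenosine scans will be taken after the drug effect has gone, or that the primary endpoint is invalid. The documents do not support that: the scan is meant to be under stress, and nothing in them says how fast flow falls once the infusion stops. A reader might also infer a distorted comparison of hypertrophic with idiopathic dilated cardiomyopathy. The agent is randomised, so no systematic effect on that contrast is expected.

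The contrast conflict alone does not disturb coronary sinus flow either, since both sections put that scan after perfusion and regadenoson reversal waits for it. With 40-50 beats, the overview timeline is less tight than with 60.

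Two things remain. A figure or a reference might supply a stop rule, but it would not make the two written contrast times or beat counts agree. And the 3 minutes is a written dose instruction which, taken literally, works against the stated intent on the details timeline and leaves little or no room on the overview's.

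**Conclusion.** The point holds as an internal inconsistency with a possible effect on the primary measurement. The contrast times differ by 60-120 s (adenosine) and 90-180 s (regadenoson), which needs no assumption, and the beat counts differ as well. The statement that 3 minutes does not reliably cover the scan rests on the assumed heart rates, on imaging starting with contrast (overview timeline only), and on an unstated scan length.

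Harm arises only if staff stop at 3 minutes. Its direction would then be toward more MVD in the adenosine half, which would raise absolute prevalence even though randomisation protects the comparison between cardiomyopathies. Its size cannot be computed from the documents. This is a cheap improvement, of minor to moderate severity.

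**What to change.** 1. Use one contrast time per agent in both sections. The overview's times (2 minutes into adenosine; 1-1.5 minutes after regadenoson) are the natural choice. Amend item (3) so that the table is in by then.
2. Use one stress perfusion length in both sections. Sixty beats keeps the match with rest perfusion in step 13.
3. Replace the fixed 3 minutes with adenosine continued until the stress coronary sinus acquisition is complete, mirroring the regadenoson reversal rule.
4. Optionally, record the infusion stop time and the coronary sinus scan end time, so that adherence can be checked.

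The cost is protocol wording and a slightly longer monitored infusion: about 0-35 s beyond 3 minutes on the overview timeline, at 60-100 bpm and with the assumed 15-35 s for set-up and scan. If Figure 3 or the references already give a stop point, item 3 only needs to bring it into the text.
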